3. Participant will be asked to provide pain level on 11-point (0-10) NRS immediately before study drug ingestion as the baseline pain score. Baseline symptoms (sedation and dizziness) will also be recorded.
4. Women will ingest the assigned gabapentin 600 mg or placebo
 - a. Stratified block randomization will occur to achieve even distribution of women based on vaginal parity (no prior vaginal delivery versus one or more prior vaginal deliveries). This strategy will ensure similar numbers of women with vaginal parity between gabapentin and placebo groups as this may be an important factor influencing pain with dilators in general.
 - b. A UC Davis Investigational Drug Services (IDS) pharmacist will use computer-generated randomization to place active or placebo treatment in two groups of sequentially numbered vials (to account for block randomization based on parity)
5. The physician will proceed with dilator insertion via our existing standardized method (including standard cervical anesthesia with 1% xylocaine 20 mL, standard number of dilators based on gestational age). Number of dilators and any pharmacologic means of cervical preparation are already reported in a standardized template and will be available for chart review.
6. Post-dilator pain will be assessed via NRS at five minutes after dilator insertion. Additional symptoms (sedation and dizziness) will be recorded.
7. Women will be discharged home with:
 - a. One additional study medication (Gabapentin 600 mg or placebo) to take at home 8 hours after the initial dose. This medication will be labeled by the IDS and completed by administering physician.
 - b. Standard prescriptions for acetaminophen 300 mg/codeine 30 mg and ibuprofen 800 mg to take as needed.
 - c. A reminder form that includes 24-hour research contact information, the times when they can expect text messages, a reminder to take the home dose of their assigned study medication at 8 hours after dilator insertion (exact time will be written out) and a reminder to bring the empty study medication bottle with them when they present for their procedure the next day.
 - d. Recommendation that they have a ride to and from abortion procedure the subsequent day.
8. Participants will be sent a baseline text message from the study phone prior to leaving the clinic. Participants will be encouraged to enable privacy features on their personal phone. Examples of security features will be reviewed and included in the consent.

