9. Participants will be contacted via text message at 2, 4, and 8 hours after dilator insertion.
 - a. Text messages will originate from a password protected study cell phone. Android application "SMS scheduler" will be used to send standardized text messages to the participant at pre-programed time intervals from time of dilator insertion.
 - b. Text message content:
 - i. Current NRS pain score
 - ii. Inventory of analgesic use since last contact
 - iii. Presence of symptoms (sedation and dizziness)

PROTOCOL TITLE: Gabapentin for pain control after osmotic dilator insertion and prior to D&E procedure: a randomized controlled trial

- iv. Reminder to take the assigned study medication (at 8 hours only)
10. Upon admission to the pre-operative ward prior to D&E, we will document the time and assess the current NRS pain score, additional analgesic use since 8 hour text message contact, and presence of symptoms (sedation and dizziness)

Blinding

Participants and providers will be blinded to study drug allocation as all study drug will be prepared by the pharmacist and placed into numbered drug bottles.

Privacy protection

Participant privacy is another ethical concern in this study. Participants may have people with access to their cell phones who do not know about the pregnancy or abortion. Compromising a woman's privacy about this matter could put her at risk depending on her life situation. To prevent this, I plan to use generic language that does not identify the context of the woman's care. Women will be counseled regarding their ability to rescind their participation at any point. Below is the verbatim content of each text message that will be sent to participants. These text messages will be sent in order, with a programmed one-minute interval between each question:

1. "What is your current pain level on a scale of 0-10? (Zero is no pain and ten is the worst pain imaginable)"
2. "How many pills of ibuprofen have you taken since the last text?"
3. "How many pills of acetaminophen with codeine have you taken since the last text?"
4. "Do you feel more dizzy than usual?"
5. "Do you feel more tired than usual?"

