Interest in gabapentin for perioperative pain management is increasing in part due to its favorable safety profile. There are few contraindications to gabapentin use. It is excreted by the kidneys unchanged from its ingested form. [26] The absence of hepatic metabolism enables use in patients with hepatic disease or on medications that influence hepatic enzymes. [26] Renal insufficiency can increase the clearance time of gabapentin so dosage adjustment or avoidance of gabapentin is needed depending on the severity of renal disease. [26] Gabapentin is well tolerated in the pediatric population as well. [26] Most common side effects include dizziness and somnolence with less common reporting coordination or balance issues, peripheral edema, or gastrointestinal symptoms. [26] These reports are among chronic users of gabapentin. Studies investigating perioperative use focus more on immediate side effects experienced by gabapentin naïve patients such as dizziness and somnolence. [26]

Study drugs will be obtained from the UC Davis Investigational Drug Services (IDS). The IDS is a division of UC Davis Pharmacy Services that can procure gabapentin and over-encapsulate it to match an identical placebo. The IDS controls participant randomization, maintains randomization log, and provides additional support for study drug administration along with accountability and adherence with state drug dispensing regulations. The IDS has already reviewed this research study and has formulated a plan for study execution with investigators. [name] (Senior IDS Pharmacist) has shadowed the Principal Investigator in the preoperative clinic to formulate a concrete plan for IDS drug preparation and medication accountability.

Participant Compensation:

Participants will be compensated \$30 for initial study drug ingestion and completing baseline data collection. They will be provided based on fully answering all five text messages at each scheduled encounter. Compensation will include an additional \$10 for completion of 2 hour and 4 hour text messages, and \$20 for the 8 hour contact. Participants will receive a final \$30 for completion of the assessment when presenting for D&E. Compensation will occur via gift cards provided to participants when presenting for their procedure the subsequent day. Maximum compensation per participant will be \$100, with partial compensation possible based on participation level. Participants will be provided with the compensation levels.

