Prior to first contact, the research assistant will program the participant into the phone contact list with their study number and preferred phone number. The Android SMS Scheduler application will record all scheduled and sent text messages. The application's template function will be used to ensure all outgoing text messages are uniform. Incoming text messages are returned to the cell phone's default text message application. The study cell phone will only be connected to the password protected, secure institutional wireless internet connection. The study cell phone's mobile data will be turned off at all times to improve security. Text message responses will be input into the study database on a weekly basis and the participant's contact information and text messages deleted from the phone.

9) Data Banking

The entire research study database, which will contain only de-identified data, will be banked indefinitely for the purposes of future research analysis.

10) Provisions to Monitor the Data to Ensure the Safety of Subjects

- Safety data will be collected throughout the study – participants will be asked about potential medication side effects.
- Adverse event (AE): adverse experience such as symptom, physical exam finding, or worsening of a preexisting condition that has a temporal association with research participation. Causal relationship with study treatment is not necessary to designate an AE.
- Given the contact of participants via text message in this study, significant breach in participant privacy will also be classified as an adverse experience. At enrollment, participants will be counseled to ensure they are making a fully informed decision to participate knowing that there will be text message contact with them. They will be counseled regarding ways to withdrawal if safety becomes a concern. If this occurs, study staff will list safety-related withdrawal as an AE and review as below.
- Serious adverse event (SAE): adverse event that requires hospitalization, causes significant disability, is life threatening or results in death.
- AEs will be logged and reviewed by an investigator for study drug relationship
- Any SAE will be reported to the principal investigator once identified. The participant will be managed medically as indicated. All source data will be

PROTOCOL TITLE: Gabapentin for pain control after osmotic dilator insertion and prior to D&E procedure: a randomized controlled trial

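### Apart from pain, no scheduled contact asks about any adverse event except sedation and dizziness, although Section 10 defines adverse events far more broadly and acts on them

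*Combined protocol and SAP*

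**What the plan says.** Section 10 (safety monitoring) opens with a general promise that "participants will be asked about potential medication side effects". It defines an AE as an "adverse experience such as symptom, physical exam finding, or worsening of a preexisting condition that has a temporal association with research participation", and adds that no causal link to treatment is needed. A significant breach of privacy also counts. AEs are to be logged and assessed for relationship to study drug. Concern about single events or about trends leads to further review and possible termination. Section 12 (study medication risk) likewise promises close monitoring of side effects and of any AE or serious AE.

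Section 7 (Procedures Involved) sets out what is asked:

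- Step 3, baseline: "Baseline symptoms (sedation and dizziness) will also be recorded".
- Step 6, five minutes after insertion: "Additional symptoms (sedation and dizziness) will be recorded".
- Step 9, texts at 2, 4 and 8 hours: the symptom item is "Presence of symptoms (sedation and dizziness", in brackets. The verbatim script under Privacy protection has five questions: pain, two analgesic counts, dizziness and tiredness. Section 12 (privacy risk) rules out any other text content.
- Step 10, pre-operative admission: pain, analgesic use "and presence of symptoms (sedation and dizziness", again in brackets.

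Section 2 describes this last contact more loosely, as an assessment of side effects.

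**The concern.** The definition in Section 10 and the questions in Section 7 do not match. The division's review works from the AE log, and its decision to look further or to consider stopping depends on what reaches that log. Only two symptoms reach it by systematic questioning.

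Three features sharpen this:

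- **Privacy.** A privacy breach is the AE most specific to this design, because women are texted at home about a sensitive matter. No contact asks whether one occurred.
- **Second dose.** The home dose falls due at about the time of the 8-hour text, which carries the reminder to take it. The pre-operative interview is therefore the only scheduled contact that can cover the period after that dose.
- **Time window.** The two symptom questions in the texts are in the present tense, and step 10 records whether symptoms are present. Only analgesic use is explicitly asked about over the interval since the previous contact. A fall, a vomited capsule or a call to an outside clinician that was over by morning has no question that would bring it out.

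**Working it through.** The plan gives no event rate or safety power, so there is no figure to reproduce. The main check is a count of what is asked.

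**Step 1. Safety content of each scheduled assessment (Section 7).**

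| Assessment | Symptoms asked | Analgesic use asked | Open AE question |
|---|---|---|---|
| Baseline (step 3) | sedation, dizziness | no | no |
| 5 minutes (step 6) | sedation, dizziness | no | no |
| 2 h text (step 9) | sedation, dizziness | yes | no |
| 4 h text (step 9) | sedation, dizziness | yes | no |
| 8 h text (step 9) | sedation, dizziness | yes | no |
| Pre-operative (step 10) | sedation, dizziness | yes | no |

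Pain is scored at all six. The same two symptoms are asked at 6 of 6 assessments, and an open question at 0 of 6.

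**Step 2. Other routes by which an AE could be recorded.**

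- Section 11: women who withdraw are asked the reason, expressly to detect AEs.
- Section 10: staff list a safety-related withdrawal as an AE, and examination findings count, so clinicians can contribute.
- Section 8 (Data Management): the research line forwards at night to the on-call family planning attending or fellow, all of whom are to be trained as study personnel.

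The first two bullets cover withdrawals and what a clinician happens to see. The third needs the woman to call. None puts a question to a woman who completes the study.

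**Step 3. Illustration of size.** Inputs: 121 women (Sections 5, 6 and 8), so about 121/2 ≈ 60 on gabapentin. The true rate p of an unasked event and the share s that is recorded are assumptions, not document figures.

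Expected recorded cases = 60 × p × s. Chance of at least one = 1 − (1 − p × s)^60.

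- p = 5%, s = 1: 3.0 expected; 1 − 0.95^60 = 0.954
- p = 5%, s = 0.5: 1.5 expected; 1 − 0.975^60 = 0.781
- p = 5%, s = 0.33: 0.99 expected; 1 − 0.9835^60 = 0.631
- p = 2%, s = 1: 1.2 expected; 1 − 0.98^60 = 0.702
- p = 2%, s = 0.5: 0.6 expected; 1 − 0.99^60 = 0.453
- p = 2%, s = 0.33: 0.40 expected; 1 − 0.9934^60 = 0.328

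For a commoner event the chance of missing it altogether is smaller: at p = 10% the figures are 0.998 (s = 1) and 0.954 (s = 0.5). The case s = 1 assumes that one open question captures every event, so the gain shown is an upper bound.

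**The case against.** The strongest reply is that the two items were chosen for a reason. Section 7 (Study drug) does mention "less common reporting coordination or balance issues, peripheral edema, or gastrointestinal symptoms", but attributes those reports to chronic users and says that perioperative studies in gabapentin-naive patients concentrate on dizziness and somnolence. Section 12 adds that studies reporting side effects most often ask about these two, and that the label's risks do not fit this setting. For two doses overnight, that is a fair basis for which symptoms to solicit. It stands as far as it goes, but the AE definition in Section 10 is not limited to expected drug effects.

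It can also be said that only the texts are scripted word for word, that Section 12 presents the two symptoms as included among those monitored, and that Section 2 speaks of side effects at the last contact, so staff could ask more. They could, but step 10 does not tell them to, and unplanned questions would vary between interviewers.

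Timing is a practical objection. This version is dated 01/11/2018 and the enrollment goal ended in January 2018. If recruitment kept to that goal, a new question would reach few women. The documents do not say how many had been enrolled.

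A reader might infer three stronger things, none of them supported:

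- *That every other AE is recorded only if a woman volunteers it.* The routes in Step 2 of the working rule this out.
- *That AE counts cannot be compared between arms.* Participants and providers are blinded and both arms get the same questions. Spontaneous reporting then makes counts low and imprecise; it biases the comparison only if reporting differs by arm, and nothing in the documents shows that.
- *That Section 3 names nausea and vomiting as a harm left unasked.* It reports a decrease in both in the hysterectomy studies.

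**Conclusion.** The point holds in limited form. For women who remain in the study, AEs beyond sedation and dizziness (and pain) are not systematically solicited. They are therefore likely to be under-counted in both arms, and the review that could lead to termination is less sensitive than Section 10 implies. Privacy breaches are included in this.

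That conclusion rests on the text of Section 7 and on the ordinary expectation that some events go unreported when nobody asks. Its size is not known. The 95% against 63% (5% rate) and 70% against 33% (2% rate) are illustrations under assumed rates and reporting shares, and they describe detection of a single case in one arm, not the comparison between arms. No primary outcome, power figure or stated analysis is affected.

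**What to change.** Add one neutral open question to the step 10 pre-operative interview, asked in the same words of every participant by blinded staff. It should cover any other problem since the first study capsule, including any privacy problem, and any call to or visit with a clinician, with the time of onset. Log the answers as AEs under Section 10 and tabulate them by arm, separately from the solicited sedation and dizziness items. Reconcile the side-effect wording in Sections 2 and 10 with step 10.

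The cost is one question in an interview that already takes place and one line on the case report form. Because it is asked in person, the text script and its privacy safeguards are untouched. There are two downsides. More minor events will have to be logged. If the question is introduced after enrollment has begun, ascertainment will be mixed across the cohort, so events should be reported by the version of the interview used.

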Based on our current volume, we estimate that we will complete enrollment of 121 women in 12 months (goal of February 2017 – January 2018). Between August 2015 and June 2016, the clinical Family Planning fellow completed 228 D&E from 15 weeks 0 days to 23 weeks 6 days gestational age (on date of procedure) at the UC Davis Medical Center. Completion of the primary analysis will occur by March 2018.

6) Study Endpoints

The primary study endpoint is enrollment of 121 total participants. The study will be reviewed at least monthly to monitor for adverse events that would indicate safety issues and thus a safety-related endpoint. Adverse events will include both

PROTOCOL TITLE: Gabapentin for pain control after osmotic dilator insertion and prior to D&E procedure: a randomized controlled trial

medical concerns and patient privacy concerns given text message contact at home.

7) Procedures Involved

Recruitment will occur in the Division of Family Planning pre-operative clinic held once to twice weekly in the Lawrence J. Ellison Ambulatory Care Center of the UC Davis Department of Obstetrics and Gynecology. This clinic is specifically for patients seeking abortion procedures. Family Planning physicians and/or research assistants will obtain informed consent from eligible women that opt to participate (all family planning attendings and fellows will be trained as study personnel). An institutional HIPAA Authorization form will also be obtained to allow access to participant's medical record for information related to the study. Study information will include demographic traits and information from dilator placement.

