PROTOCOL TITLE: Gabapentin for pain control after osmotic dilator insertion and prior to D&E procedure: a randomized controlled trial

8) Data and/or Specimen Management and Confidentiality

Sample size calculation

For the purpose of calculating sample size, there is no existing data that truly mirrors the objective of this study (context of pain, use of NRS, and use of change in pain score from baseline). The closest approximation is the mean immediate post-dilator insertion pain score of 5.2 (SD 1.2) via NRS from Borgatta, et al (2012). However, when using this data point and a commonly cited clinically significant decrease in NRS pain score of 2 points, computation with SAS 9.1 (factoring in power at 80% ($\alpha=0.05$), normal distribution) yielded a small sample size of only 12 women per group. [27-33] Based on the block randomization there are four groups for a total of 48 women. To account for up to 20% of subjects not responding to text messaging for the primary outcome the sample size estimate will increase to 58 total women. To ensure we gather sufficient data to truly outline pain experience during the dilator-procedure interval, we will more than double the sample size to recruit 121 women. We will stratify these 121 women by presence or absence of prior vaginal parity. Ensuring similar distribution of vaginal parity between the gabapentin and placebo groups is important as vaginal parity may affect pain with osmotic dilators.

Statistical Analysis

We will use non-parametric testing to assess the primary outcome variable because we do not expect normal distribution of the data. Chi square analysis and fisher exact tests will be used to compare demographics and dichotomous variables as appropriate. I plan to describe the pain course for the total study cohort using means and medians as appropriate.

Data Management

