reviewed. Physician investigators will assess for causality or relatedness of the adverse experience to the study.

- In accordance with UC Davis institutional review board (IRB) reporting policy, AEs will be reported at annual IRB renewal submission. SAEs that are unanticipated and thought to be related to the study (thereby placing research subjects at higher risk of harm than originally thought) will be reported to the IRB by the principal investigator within five days of becoming aware of the event.
- The study will be reviewed semimonthly at the Family Planning division research meeting, which includes all research staff. Any concerns regarding individual or trends in AEs will prompt further review of the study and consideration of study termination.
- Study allocation will remain concealed except in a scenario in which revealing allocation is clinically important for the participant's management

11) Withdrawal of Subjects

Based on the safety of existing research on both gabapentin for peri-procedure pain and an existing abortion-related study using text messaging of subjects, we do not anticipate frequent circumstances for participant withdrawal. There are both investigator and participant-initiated modes for subject withdrawal. Participants will be withdrawn from the study pending investigator review of AE that warrants removal or any SAE (see Section 10). Participants will be counseled at enrollment about how to withdrawal themselves from the study for any reason. If a participant is withdrawn from the study, no further data will be collected. We will inquire about the reason for withdrawal so we can monitor for AE/SAE.

12) Risks to Subjects

There are two primary categories of risk in this study:

1. *Study medication risk (Gabapentin):*

As noted in Section 7, Gabapentin is a safe, well tolerated medication that is an established agent of interest for peri-procedure analgesia. Contraindications and medication interactions are few. This study will be monitoring for the more common side effects that can happen (though not frequently in prior studies), including increased self-reported sedation and dizziness from baseline.[25]

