The FDA label for gabapentin lists adverse events reported by studies investigating the drug for management of either epilepsy or postherpetic neuralgia. Both FDA approved indications for gabapentin use a wide range of drug dosing and a significantly longer duration compared to this study. Studies investigating gabapentin for peri-procedure analgesia are powered to detect their primary outcome of pain reduction. Those studies reporting side effects ask about sedation and dizziness most commonly. [34] Gynecologic studies, typically in the context of abdominal hysterectomy, report no statistically significant increase in sedation or dizziness compared to placebo. [13-14] Both studies started with initial doses of gabapentin 1200 mg, which is twice the dosing of this study.[13-14] Dierking et al continued gabapentin dosing for a total of 3000 mg over 24 hours (year). While

PROTOCOL TITLE: Gabapentin for pain control after osmotic dilator insertion and prior to D&E procedure: a randomized controlled trial

participants may be able to understand the FDA risk stratification, delineating frequent, infrequent, and rare adverse events, the risks in the label do not accurately simulate the clinical context of this study.

To minimize risks, the dose of Gabapentin used in this study is comparable to that of prior peri-procedure studies and the same as an ongoing randomized controlled trial through the family planning division at Emory University that is investigating Gabapentin 600 mg versus placebo for pain control during first trimester aspiration abortion. [25] Out of caution, participants will be required to have a ride home from the clinic as criteria for study eligibility so they aren't driving after study medication dosing. Frequency of reported side effects will be closely monitored, as well as any AE or SAEs, per Section 11.

2. *Privacy risk:*

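### Privacy harm is a named primary risk and a significant breach counts as an AE, but none of the six scheduled assessments asks about it, so it is ascertained only passively, and the AE review criterion and IRB timing do not fit it

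*Combined protocol and SAP*

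**What the plan says.** The protocol treats privacy as a main hazard of the trial. Section 12 opens with "There are two primary categories of risk in this study": the study medication and privacy. The privacy text in Section 7 gives the reason: "Compromising a woman's privacy about this matter could put her at risk depending on her life situation". Section 6 counts as adverse events both "medical concerns and patient privacy concerns given text message contact at home". Section 10 repeats this with a threshold: a "significant breach in participant privacy will also be classified as an adverse experience". The word 'significant' is not defined, and Section 6 has no such threshold.

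On active safety questioning, Section 10 mentions only possible side effects of the medication. Section 7 lists the content of each contact and gives the five texts word for word, and Section 12 says that nothing beyond those texts will be sent.

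On handling, Section 10 has an investigator review logged AEs for a link to the study drug. It defines an SAE as an "adverse event that requires hospitalization, causes significant disability, is life threatening or results in death". For the IRB, "AEs will be reported at annual IRB renewal submission", while a five-day report is kept for SAEs that are both unanticipated and thought related. The section says that these rules follow the institution's IRB reporting policy. Internal review is semimonthly in Section 10 and at least monthly in Section 6.

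**The concern.** The plan looks for one of its two named harms and waits to be told of the other. Dizziness and sedation are asked about at every contact. Unwanted disclosure, which arises from the study's own procedure of texting women at home, is asked about at none.

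Two things are at stake. The first is participant safety: internal review can change or stop the text contact only if it hears of a problem. The second is how a zero count will be read. Section 12 supports the texting method partly by noting that a similar text-message trial elsewhere had reported no privacy-related adverse events. This trial's count could be cited in the same way, although no woman would have been asked.

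**Working it through.** The protocol gives no figure on this point to reproduce. The check sets the scheduled contacts and the reporting steps side by side; the arithmetic only adds context.

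**1. What each scheduled assessment asks (Section 7)**

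| Assessment | Content | Privacy item |
|---|---|---|
| Baseline, in clinic | Pain, sedation, dizziness | No |
| 5 minutes after insertion, in clinic | Pain, sedation, dizziness | No |
| 2, 4 and 8 hours, by text (three contacts) | Pain, two analgesic counts, dizziness, tiredness | No |
| Pre-operative, in person | Pain, analgesics, sedation, dizziness | No |

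Assessments with a privacy question: 0 of 6. Because Section 12 closes the list of texts, the gap is not simply a shortened description.

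**2. How a breach can still become known.** There are three routes: the 24-hour contact line (Sections 7 and 12), the question about the reason for withdrawal (Section 11), and the rule that a safety-related withdrawal is listed as an AE (Section 10). Each needs the woman to act first. A woman who stops answering has not withdrawn, and no step asks her why.

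**3. What happens once a breach is logged**
- *Individual review.* Section 10 defines an AE by its timing relative to research participation and does not require a causal link to treatment. The stated review criterion is nevertheless the study drug. A breach caused by a text message will be unrelated to gabapentin, so that review can miss the relationship that matters. The SAE step is wider and assesses relation to the study.
- *Internal meeting.* It may consider any AE concern and has no such limit.
- *IRB.* A breach with none of the listed serious outcomes is an ordinary AE and goes in at annual renewal. A breach with such an outcome is an SAE, but the five-day report also requires it to be unanticipated, which is open to argument for a risk that the protocol itself names.

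**4. Timing.** Section 5 plans 121 women in 12 months.
- 121 / 12 = 10.1 women per month.
- 121 / 24 = 5.0 women per half-month.

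A logged breach would reach internal review after about 5 further enrolments (semimonthly) or about 10 (monthly). The interval to an annual report can be up to 12 months, the length of planned enrolment; the renewal date is not given.

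**5. What asking would add.** If all 121 women were asked, every breach were disclosed and none were reported, the exact one-sided 95% upper bound would be 1 − 0.05^(1/121) = 0.0245, about 2.4%. With volunteered reports only, the share of breaches that surface is unknown and zero events give no bound.

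For illustration, let p be the breach rate and s the share of breaches that reach the record. The chance of recording at least one is 1 − (1 − p·s)^121. Both p and s are assumptions, because the documents give neither. For p = 1% and s = 25%: 1 − 0.9975^121 = 0.261.

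| p | s = 25% | s = 50% | s = 100% (all asked, all disclose) |
|---|---|---|---|
| 0.5% | 0.140 | 0.261 | 0.455 |
| 1% | 0.261 | 0.455 | 0.704 |
| 2% | 0.455 | 0.704 | 0.913 |
| 5% | 0.782 | 0.953 | 0.998 |

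**The case against.** The strongest reply is that the plan already does a good deal. The texts mention neither pregnancy nor abortion, message times are given in advance, phone privacy settings are reviewed, and a woman can stop the messages at any hour. Privacy concerns fall under regular internal review, which can lead to study termination. The trial's objective is pain at 8 hours and it plans no estimate of privacy risk, so the 2.4% bound serves no planned analysis. All of this stands. It makes a breach less likely and makes the point modest, but it does not put a privacy question into any assessment.

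Four stronger readings are tempting and are not supported.
- *Breaches will go undetected.* Detection is passive, not absent: the three routes above exist.
- *The SAE definition cannot capture a breach.* It can, if the breach leads to hospitalization, disability, a life-threatening event or death. It leaves out serious harm of other kinds, such as disclosure or coercion.
- *About 24 women (20% of 121) may fall silent for privacy reasons.* The 20% is a sample-size allowance, "To account for up to 20% of subjects not responding to text messaging", used to go from 48 to 58. The 121 was reached separately, by more than doubling 58. Nothing ties non-response to privacy, and non-responders are still due for the pre-operative assessment.
- *The IRB cannot act until enrolment is over.* If approval came before the first enrolment, a renewal would fall within a 12-month enrolment period. The IRB policy that Section 10 cites is also not available here and may require prompt reporting of breaches.

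**Conclusion.** The point holds as a gap in safety ascertainment, with a smaller gap in review and reporting. Drug side effects are solicited at every scheduled assessment and privacy harm at none. The criterion for reviewing an individual AE does not suit a privacy event, the threshold word is undefined, and for a breach without a listed serious outcome the protocol states no IRB report earlier than annual renewal.

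The documents do not contradict themselves here, and the primary pain comparison, the sample size and the treatment are untouched. This is an inexpensive improvement that should be made, not a defect that threatens the result.

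The conclusion assumes that Section 7 lists the assessment content in full. The consent and reminder forms are not in the documents; they may encourage women to report problems, but that too would depend on the woman coming forward. The breach rate and the share volunteered are unknown, so the detection probabilities show a direction and are not estimates for this trial.

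**What to change.** 1. **Section 7, pre-operative assessment.** Ask every woman in private, away from anyone accompanying her and including those who did not answer texts: did anyone see a study message, or learn about your care through the messages, when you did not want them to? If texts went unanswered, also ask whether privacy was a reason. Record all answers. Log as an AE those that an investigator judges to be a significant breach; a glance at a generic pain question need not qualify.
2. **Section 10, definition.** Define 'significant', and bring Section 6 into line with it.
3. **Section 10, review and reporting.** Review AEs for relation to study participation, including text contact, and not to the drug alone. State when a significant breach is reported to the IRB, taking the time from the IRB's own policy.
4. **Report.** Give the number of women asked as the denominator. Section 5 planned enrolment to end in January 2018 and this version is dated 01/11/2018, so if the questions start part-way, say from when.

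The cost is one or two questions at an existing in-person contact, a few sentences in Sections 6 and 10, and possibly a few more logged events. The question will not reach women who withdraw or do not present, nor a breach that surfaces after the D&E; for these the existing passive routes remain.
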